3.2.2 Safety assessments

3.2.2.1 Adverse events and common treatment responses

All AEs reported by study subjects, investigators, or other study staff after the time of informed consent through end of study will be recorded. Events will be recorded regardless of causality. Note: End of study will be 13-months from baseline treatment for subjects who receive a touch-up, 12-months from baseline treatment for subjects who do not receive a touch-up, and Month 2 for control subjects.

A subject diary will be dispensed on the day of treatment to collect CTR information as well as specific safety concerns. The diary will be collected daily for 4-weeks post-treatment. Another 4-week diary will be distributed and completed following touch-up treatment at Month 1, if applicable.

Subjects will be asked to record daily on the diary any pre-defined CTRs and other safety events that may occur. The treating investigator will review and determine if any entries should be captured as AEs. Subjects assigned to the control group will not be provided or asked to complete the diary.

After the baseline treatment, treated subjects will receive a 72-hour post-treatment phone call and return to the clinic for a 2-weeks post-injection visit. During these safety checks, the subject diary will be reviewed for potential AEs. Subjects will continue their diary for 1-month after baseline treatment. If a subject receives an optional touch-up 1-month after baseline treatment, the subject will receive a 72-hour post touch-up phone call and return to the clinical 2-weeks post touch-up. Touch-up diaries will be reviewed for potential AEs and subjects will continue to complete the diary for 1-month after the touch-up injection.

Additional information on safety assessments and procedures is discussed in [Section 7](#).

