2.2.2 Secondary endpoints

- Summary of the FACE-Q satisfaction with eyes scores for treated subjects at baseline and Month 2 post last injection (i.e., either baseline treatment or touch-up, if applicable) and for control subjects at baseline and Month 2. The subject's assessment is based on taking into consideration both eyes.
- Descriptive summary of GAIS scores for treated subjects at Month 2 post last injection (i.e., either baseline treatment or touch-up, if applicable), as completed by the treating investigator. This assessment is a measure of aesthetic improvement relative to the baseline pre-treatment condition, as assessed from photographs.
- Descriptive summary of GAIS scores for treated subjects at Month 2 post last injection (i.e., either baseline treatment or touch-up, if applicable), as completed by the subject. This assessment is a measure of aesthetic improvement relative to the baseline pre-treatment condition, as assessed from photographs.
- Summary of the responder rates in the treatment group and the control group at Month 2, according to the MIHAS, [REDACTED] using subject photographs. In addition to baseline photograph assessments, for subjects randomized to treatment, if no touch-up is performed, the photographs assessed will be those taken at 2-months post baseline injection. If a touch-up is performed, the photographs assessed will be those taken at 2-months post touch-up. For subjects randomized to the untreated control group, the photographs assessed will be taken at 2-months from the baseline visit.

Treatment response is defined as \geq 1-point improvement on both IOHs when comparing the change from baseline to Month 2. A subject will be considered a responder if a treatment response of at least 1-point change on both IOHs is determined [REDACTED].

2.2.4 *Safety endpoints*

- Incidence and nature of device- and/or injection-related AEs and SAEs observed during the study.
- Incidence, severity, and duration of pre-specified CTRs reported in subject diaries.

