5.1 Schedule of events by visit

The Schedule of Events is presented in [Appendices 10.1](#) (treated subjects) and [10.2](#) (control subjects).

Day 0 (-28 Day) – Baseline Treatment (BT) / No Treatment (Control) includes Screening, Enrollment, and Baseline Assessments

[figure not shown]
The following procedures will be performed at this visit in the following order:

- Obtain written informed consent. A subject must be informed of the study requirements, including the risks and benefits of participation. An IEC/IRB-approved informed consent must be signed and dated by the subject prior to any study related activities or procedures being performed, including discontinuation of any prohibited medications.
- Assign subject identification.
- Collect demographic information.
- Collect height and weight. Height will be collected at the baseline visit only.
- Record medical history.
 - Record ocular history.
- Review and record concomitant medications/therapies.
- Perform urine pregnancy test (if female of childbearing potential). Negative test required prior to randomization.
- Confirm subject meets all eligibility criteria.
 - Treating physician confirms that the subject meets all eligibility criteria prior to randomization.
- Take standardized baseline IOH photographs.
- [REDACTED] perform the MIHAS assessment.

[figure not shown]
- Visual safety assessments on both eyes.
 - Visual acuity test (using a Snellen chart);

- Visual field test;
- Ocular motility exam; and
- Fundoscopic (ophthalmoscopic) view of the eye (not dilated).
- Administer FACE-Q assessments to subject.
- Satisfaction with eyes

- Randomize subject.

NOTE: Subjects randomized to the control group (no treatment) have completed this visit and will be scheduled for the Month 2 visit.

- Injection (for subjects randomized to the treatment group):
 - Administer treatment injection **to first IOH**.
- Wait 30 minutes.
- Perform visual safety assessments on first eye (where IOH area was treated).
- Administer treatment injection to second IOH if treating investigator agrees that it is safe to proceed with injecting the second IOH.
- Wait 30 minutes.
- Perform visual safety assessments on other eye (where second IOH area was treated).
- Dispense subject diary and discuss completion instructions.
- Review and record AEs.
- Schedule 72-hour follow-up phone call and Week 2 visit.

Follow-up Phone call (72-hours ±1 day post treatment)

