7 SAFETY AND ADVERSE EVENTS

7.1 Definitions

7.1.1 *Investigational medical device*

An investigational medical device is defined as a medical device being assessed for safety or effectiveness in a clinical investigation. This definition includes medical devices already on the market that are being evaluated for new intended uses, new populations, new materials, and/or design changes. In this protocol, the terms “investigational medical device” and “investigational device” are used interchangeably.

7.1.2 *Adverse event (AE)*

An AE is defined as an untoward medical occurrence, which does not necessarily have a causal relationship to the investigational medical device. An AE can therefore be any unfavorable, unintended, or untoward clinical sign (including an abnormal laboratory finding), unintended disease or injury, and/or a symptom or disease temporally associated with the use of the investigational medical device, whether or not considered related to that investigational medical device.

- Definition includes events related to the investigational medical device or the comparator.
- Definition includes events related to the procedures involved.
- AEs may include, but are not limited to, subjective or objective symptoms spontaneously offered by the subject, uncovered by review of concomitant medications or therapies, and/or observed by the investigation-site staff. The investigator will determine the description (sign, symptom, or diagnosis), onset, outcome, seriousness, severity, cause, and action taken for any event.

In cases of surgical or diagnostic procedures, the condition/illness leading to such a procedure is considered as the AE, rather than the procedure itself.

Pre-existing conditions that do not worsen during the course of the clinical investigation are not reportable as AEs. Recurring symptoms associated with pre-existing conditions are not considered AEs unless they have a clinically significant increase in severity and/or frequency. To determine whether a condition has worsened, it is compared to the condition of the subject at screening.

Elective treatments planned before screening, which are documented in the subject's source data, are not typically regarded as AEs. The subject's course must be monitored

until the event has subsided, or in a case of permanent impairment, until the event stabilizes and the overall clinical outcome has been ascertained.

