- Any serious adverse effect which by its nature, severity, or degree of incidence or outcome has been identified in the risk analysis report, IB, or product labeling.

7.1.8 *Common treatment responses (CTR)s*

CTRs are common clinical presentations and/or side effects that a study subject may experience following treatment. Subjects will self-report CTRs, as defined *a priori* in the protocol, on a diary provided to them. The treating investigator will review the diary and determine if any diary entries should be captured as AEs. A CTR that is more severe than what is generally expected and/or is not resolving should also be evaluated by the investigator as a possible AE or SAE. CTRs include the following: swelling; visible lumps; bumps you can feel; bruising or discoloration; redness; rash; pain/discomfort (including burning/stinging); itching; blistering/peeling skin; and/or scabby/crusty skin.

Treated subjects will be instructed (within the diary) to seek immediate medical attention if any of the following symptoms are observed: changes in vision; fever; dizziness;

confusion; weakness in arms/legs; changes in alertness/consciousness; difficulty speaking; face droop; change in skin color comparing one side to the other; a blue or white spot of skin; and/or a headache that is more intense or longer than you usually experience. They will also have the opportunity to self-report any unforeseen/unanticipated events on the diary.

7.1.9 *Device deficiency*

A device deficiency is defined as any inadequacy of a medical device with respect to its identity, quality, durability, reliability, safety, or performance. Device deficiencies include malfunctions, use errors, and inadequate labeling.

Device deficiencies include events that did not lead to an AE, but could have led to a medical occurrence if suitable action had not been taken, if intervention had not been made, or if circumstances had been less fortunate.

All device deficiencies shall be documented and reported by the PI throughout the clinical investigation and appropriately managed by Merz North America, Inc. in accordance with [Sections 7.2.4.3](#) and [7.3](#).

7.1.10 *Malfunction*

Malfunction is defined as failure of an investigational medical device to perform in accordance with its intended purpose, when used in accordance with the product labeling or the protocol.

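### Common treatment responses (CTRs) have no visible pre-injection record, so under-eye signs already present can be counted as responses and can lengthen CTR durations

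*Protocol*

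**What the plan says.** Protocol 2.2.4 and SAP 6.2 list two safety endpoints. The second is "Incidence, severity, and duration of pre-specified CTRs reported in subject diaries".

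Protocol 7.1.8 defines the concept by timing alone: "CTRs are common clinical presentations and/or side effects that a study subject may experience following treatment". Its list of terms includes "swelling; visible lumps; bumps you can feel; bruising or discoloration; redness; rash", and goes on to pain, itching and skin changes.

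Protocol 3.2.2.1 covers collection: "A subject diary will be dispensed on the day of treatment to collect CTR information as well as specific safety concerns". It continues: "Subjects will be asked to record daily on the diary any pre-defined CTRs and other safety events that may occur". In the Day 0 sequence of Protocol 5.1, the step "Dispense subject diary and discuss completion instructions" comes after both injections and the eye checks that follow them. Controls receive no diary. For touch-ups, 3.2.2.1 adds: "Another 4-week diary will be distributed and completed following touch-up treatment at Month 1, if applicable".

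For adverse events, Protocol 7.1.2 has a filter, with worsening judged against screening: "Pre-existing conditions that do not worsen during the course of the clinical investigation are not reportable as AEs". No matching sentence is visible for CTRs.

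On analysis, Protocol 8.4.2 plans a descriptive summary of diary CTRs, and 8.6.2 leaves the detailed CTR rules to the SAP. The visible SAP names CTRs as an endpoint but gives no CTR rule. Its safety imputation section (7.4.1.2) deals only with adverse events. Parts of SAP 7.2 and all of 7.3 are not shown.

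**The concern.** Several listed signs can be present under the eye before any injection, discoloration and swelling above all. A diary that starts after the injection cannot show by itself whether such a sign is new. Without control diaries there is no background rate to set against it. The investigator's diary review does not close the gap, because it decides whether an entry also becomes an adverse event, not whether it stays in the CTR data.

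Other measures in this trial have a pre-injection reference: MIHAS and FACE-Q are taken on Day 0, GAIS uses baseline photographs, and the eye examinations are compared with baseline. CTRs have none that is visible.

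At stake is the CTR profile that the pilot passes on to the pivotal study (Protocol 2.1). An unchanged sign entered every day adds a case to incidence and appears as a response lasting the whole 28-day diary.

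**Working it through.** The documents state no CTR rate and no prevalence of pre-existing signs, so there is no planned figure to reproduce. The check has three parts.

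**1. What could separate old from new signs**

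| Possible source | What the text gives | Is it enough? |
|---|---|---|
| Diary before injection | Dispensed after both injections (5.1) | No |
| Control diary | None (3.2.2.1) | No |
| Pre-existing-condition rule | Adverse events only (7.1.2) | No |
| Medical and ocular history | Taken on Day 0, not itemised by CTR (5.1) | In part |
| Baseline photographs | Taken on Day 0, not linked to CTR scoring (5.1, 3.2.1.2) | In part: visible signs, but not pain, itching or palpable bumps |
| Status before touch-up | First diary kept until the Month 1 visit (5.1) | Largely, if a rule uses it |

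**2. Effect on incidence**

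Inputs: 44 treated subjects (Protocol 4.1); true treatment-caused incidence *p* and pre-existing prevalence *q*, both assumed. The model takes the two as independent and supposes that every pre-existing sign is entered in the diary.

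- Observed incidence = 1 − (1 − p)(1 − q)
- Net excess in subjects = 44 × q × (1 − p)

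Example: p = 0.10 and q = 0.30 give 1 − 0.90 × 0.70 = 37% observed, and 44 × 0.30 × 0.90 = 11.9 extra subjects.

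| True incidence p | Observed incidence, q = 5% to 30% | Excess, q = 5% | q = 10% | q = 20% | q = 30% |
|---|---|---|---|---|---|
| 10% | 14.5% to 37% | 2.0 | 4.0 | 7.9 | 11.9 |
| 30% | 33.5% to 51% | 1.5 | 3.1 | 6.2 | 9.2 |
| 60% | 62% to 72% | 0.9 | 1.8 | 3.5 | 5.3 |
| 90% | 90.5% to 93% | 0.2 | 0.4 | 0.9 | 1.3 |

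The excess matters for less frequent CTRs and nearly vanishes for very common ones.

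**3. Effect on duration**

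Protocol 1.2 reports that earlier injection-site responses cleared within 7 days. As an illustration at the upper end, suppose all 44 subjects have a 7-day response, and k of them also enter a pre-existing sign on all 28 days, so that their recorded duration is 28 days.

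- Mean duration = [7 × (44 − k) + 28 × k] / 44 = 7 + 21k/44
- k = 4: 8.9 days, with 4/44 = 9% lasting beyond 7 days
- k = 9: 11.3 days, with 9/44 = 20% beyond 7 days
- k = 13: 13.2 days, with 13/44 = 30% beyond 7 days

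Here incidence is 100% with or without the pre-existing signs. Duration is distorted even where incidence is not.

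**The case against.** The strongest reply is that neither the diary form nor its completion instructions are in the documents, and no CTR counting rule is visible. The form may ask only for new or changed signs. A counting rule may sit in the SAP text that is not shown, the Day 0 list has a gap after the MIHAS step, and most exclusion criteria are redacted and may keep out people with existing conditions at the site. All of this stands as a limit on what can be claimed. A reader might infer that pre-existing signs will be counted as responses; the documents support only that they can be. A hidden SAP rule would not fill the collection gap, though, because it cannot use a Day 0 status that was never recorded.

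A reader might also infer that signs left from the first injection are counted twice after a touch-up, beyond repair. The documents do not support this. Daily entries run to the Month 1 visit, so status before the touch-up is recorded, apart from up to about 3 days if that visit falls late in its Day 28 (+3 days) window. Whether anything is counted twice depends on whether counts are per diary or per subject. Only a visible rule for using the two diaries together is missing.

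Nor does it follow that 2 to 13 of 44 subjects would be false cases. Those figures are 44 × q for q from 5% to 30% (2.2 to 13.2). They are an upper bound that applies only if no subject with an existing sign also has a true response.

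Finally, Protocol 8.4.2 rests the safety assessment mainly on adverse events and serious adverse events, CTRs are only described, and photographs give partial evidence for visible signs. This limits the consequence but does not remove it.

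**Conclusion.** The concern holds as a modest, correctable weakness in one safety endpoint. With no visible pre-injection CTR record, no control diary and no pre-existing-condition rule for CTRs, existing under-eye signs can enter the CTR results. For Day 0 status this cannot be fully recovered later, because photographs and history do not capture pain, itching or palpable bumps.

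The size is unknown. The figures rest on an assumed prevalence of 5% to 30%, independence, and complete entry of existing signs. On that basis the net excess is about 2 to 12 of 44 subjects at a true incidence of 10%, 1 to 5 at 60%, and about 1 or fewer at 90%. The bias falls mainly on duration and on the less frequent CTRs. The primary endpoint and its power are not affected.

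**What to change.** **Protocol 5.1, Day 0:** treated subjects complete the CTR page of the diary once, before the first injection.

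**SAP, safety section:** report all diary CTRs as recorded and, separately, those that are new or more severe than on the pre-injection page. For a touch-up diary, use the last day of the first diary as the reference; no extra page is needed at Month 1.

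**Report:** state that CTR incidence has no concurrent control. No control diary is proposed, because a within-subject reference answers the question of what was already there. For any subject already injected without the page, Day 0 status stays unknown and the report should say so.

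**Cost:** a few minutes of subject time at a visit already attended, and one extra derivation. No added visit or procedure.

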3.2.2.2 Visual safety assessments

Although the incidence of SAEs associated with retinal artery occlusion is very low, treated subjects will undergo visual examinations to potentially identify several associated ophthalmic signs and/or symptoms that may represent ophthalmic artery occlusion.

All injecting physicians will be oculoplastic surgeons. In addition to plastic surgery expertise, these physicians have all completed ophthalmology training and have the knowledge and skill set specifically suited to injecting and treating issues in this anatomic area.

For subjects assigned to the treatment group, prior to injection, each subject will undergo a series of bilateral, visual safety assessments. These assessments will also be completed post injection at Week 2 and Months 1, 2, 3, 6, 9, and 12 after the last injection (i.e., either baseline treatment or touch-up, if applicable). If subjects received a touch-up 1-month after the baseline injection, a visual assessment will be performed immediately post touch-up. Visual assessments will include a visual acuity test (using a Snellen chart), a visual field test and an ocular motility exam. The investigator will also perform an undilated fundoscopic exam with an ophthalmoscope.

For subjects assigned to the control group visual safety assessments will be performed at baseline and Month 2.

3.2.2.2.1 Visual acuity

Visual acuity will be determined using the Snellen chart. Each site is equipped with a Snellen chart. The lane and distance from the chart will be confirmed by the monitor.

The site will follow standard directions for using the Snellen chart in determining visual acuity. The subject will be asked to cover one eye (if the subject wears glasses/contacts for distance vision they will be asked to keep them on/in). The examiner will point to each line as the subject reads the letters out loud. The smallest line where the subject identified the majority of letters correctly (i.e., if he/she could read 5 out of 8 letters on line 8, the visual acuity would be 20/20.) Visual acuity is expressed as a fraction. The top number refers to the distance the subject stands from the chart while the bottom number indicates the distance at which a person with normal eyesight could read the same line. The visual acuity per eye will be recorded in the electronic case report form (eCRF).

3.2.2.2.2 Visual field test

The Visual field test will measure how sensitive the vision is in different parts of the visual axis. To measure the visual field, the examiner will use the standard finger test according to the American Academy Ophthalmology.

3.2.2.2.3 Ocular motility exam

The examiner should determine if the subject's motility is intact in each direction of gaze. The subject should be instructed to voice if they have any double vision in any of these fields of gaze.

3.2.2.2.4 Undilated central retinal fundoscopic exam using an ophthalmoscope

In this procedure, the oculoplastic surgeon will perform a focused exam of the central retina and blood vessels to evaluate for any evidence of vascular occlusion.

After the injection of the first IOH (either baseline treatment or touch-up, if applicable), subjects will be asked to wait 30 minutes and then repeat the visual safety assessments for the already treated side. The subsequent side will then be injected once these assessments are completed on the first side and the investigator confirms that it is safe to proceed with treatment on the second IOH. The subject will then receive the Belotero Balance to treat the second IOH, wait 30 minutes, and then repeat the visual safety assessments for that side. When the subject returns for the 2-week safety follow-up visit and any subsequent visits, these visual assessments will be repeated and compared to baseline for any changes that could indicate a safety signal or concern.

NOTE: If only injecting one side for touch-up, only the side being injected will need the visual safety assessments 30-minutes post-treatment.

A local retinal specialist will be identified in advance to address any visual changes and potential retinal artery occlusion (i.e., investigator-determined, clinically significant changes in vision, such as blindness, blurriness, double vision, pain in or around the eye [other than typical injection-induced pain], blind spots, or restriction of eye motility).

3.2.2.5 Directions for intravascular injection or embolic event

In the event of intravascular injection or embolic event, the treating physician will provide prompt medical attention and follow the proper protocol for handling these symptoms. If in progress, best practices should be used to stop the injection. The treating physician should consider the following: an immediate referral to the retinal specialist, injection of hyaluronidase in the anatomic area of treatment and/or retrobulbar, and consideration of active reduction of intraocular pressure. The investigator should treat in accordance with the American Society for Dermatologic Surgery guidelines. The subject will be closely monitored by the treating investigator, and if applicable, a retinal specialist.

3.2.3 *Definitions*

3.2.3.1 *Subject enrollment and randomization*

Subjects are considered to be enrolled after they sign informed consent, meet all eligibility criteria, and are randomized in the electronic randomization system.

Screen failures are defined in [Section 4.5](#).

3.2.3.2 *Subject completion*

Subjects are considered to have completed the study if they are randomized, received treatment (for treatment group), and completed all visits defined in the Schedule of Events (see [Section 5.1](#) and [Appendices 10.1 and 10.2](#)). Control group subjects are considered to have completed the study after all Month 2 assessments have been completed.

3.2.3.3 *End of study and Total Study Duration*

Subjects will be screened and enrolled/randomized at the first study visit. For subjects randomized to the treatment group, treatment will occur at this baseline visit. The time from the baseline visit to the end of study is 13 months for subjects who receive a touch-up, 12 months for treated subjects, and 2 months for control subjects.

The primary effectiveness endpoint is at Month 2 after the last injection (i.e., either baseline treatment or touch-up, if applicable); however, treated subjects will continue to be followed-up for safety after the effectiveness endpoint via clinical visits at Months 3, 6, 9, and 12 after the last injection received (i.e., either baseline treatment or touch-up, if applicable). Additional details regarding the timing of database lock and statistical analyses are provided in [Section 8.5](#).

